## 2. ABBREVIATIONS

Abbreviations pertain to the Statistical Analysis Plan (SAP) only (not the tables, figures and listings [TFLs]).

%AUC( $t_{last}-\infty$ )	Percentage of AUC(0- $\infty$ ) extrapolated
ADA	Anti-drug antibody
AE	Adverse event
AUC	Area under the concentration versus time curve
AUC(0- $\infty$ )	Area under the concentration versus time curve from time zero to infinity
AUC(0- $t_{last}$ )	Area under the concentration versus time curve from time zero to time $t$ , where $t$ is the last time point with a measurable concentration
BQL	Below the lower limit of quantitation
CL	Apparent total body clearance of drug calculated at intravenous administration
CL/F	Apparent total body clearance of drug calculated after extra-vascular administration
$C_{max}$	Maximum observed drug concentration
CRF	Case Report Form
CRU	Clinical Research Unit
CSR	Clinical Study Report
ECG	Electrocardiogram
F	Bioavailability based on AUC(0- $\infty$ )
ICH	International Conference on Harmonisation
ISP	Injection site pain
ISR	Injection site reaction
IV	Intravenous
MedDRA	Medical Dictionary for Regulatory Activities
PK	Pharmacokinetic
SAE	Serious adverse event
SAP	Statistical Analysis Plan
SC	Subcutaneous
SD	Standard deviation

---

$t_{1/2}$	Half-life associated with the terminal rate constant ( $\lambda_z$ ) in non-compartmental analysis
TE ADA	Treatment-emergent antidrug antibody
TE ADA+	Treatment-emergent antidrug antibody positive
TEAE	Treatment-emergent adverse event
TFLs	Tables, Figures, and Listings
$t_{max}$	Time of maximum observed drug concentration
VAS	Visual analog scale
V ss	Volume of distribution at steady state following intravenous administration
V ss/F	Apparent volume of distribution at steady state after extra-vascular administration
V z	Volume of distribution during the terminal phase after intravenous administration (IV administration only)
V z/F	Apparent volume of distribution during the terminal phase after extra-vascular administration (SC administration only)
WHO	World Health Organization

### **3. INTRODUCTION**

This SAP has been developed after review of the Clinical Study Protocol (final version dated 15 May 2020), Protocol Amendment (a) (final version dated 26 June 2020), Protocol Amendment (b) (final version dated 14 July 2020), and Protocol Amendment (c) (final version dated 21 October 2020).

This SAP describes the planned analysis of the safety, tolerability and pharmacokinetic (PK) data from this study. A detailed description of the planned TFLs to be presented in the clinical study report (CSR) is provided in the accompanying TFL shell document.

The intent of this document is to provide guidance for the statistical and PK analyses of data. In general, the analyses are based on information from the protocol, unless they have been modified by agreement with Eli Lilly and Company. A limited amount of information concerning this study (e.g., objectives, study design) is given to help the reader's interpretation. When the SAP and TFL shells are agreed upon and finalized, they will serve as the template for this study's CSR.

This SAP supersedes the statistical considerations identified in the protocol; where considerations are substantially different, they will be so identified. If additional analyses are required to supplement the planned analyses described in this SAP, they may be performed and will be identified in the CSR. Any substantial deviations from this SAP will be agreed upon with Eli Lilly and Company and identified in the CSR. Any minor deviations from the TFLs may not be documented in the CSR.

This SAP is written with consideration of the recommendations outlined in the International Conference on Harmonisation (ICH) E9 Guideline entitled Guidance for Industry: Statistical Principles for Clinical Trials and the ICH E3 Guideline entitled Guidance for Industry: Structure and Content of Clinical Study Reports.

## 4. STUDY OBJECTIVES AND ENDPOINTS

### 4.1 Primary Objectives and Endpoints

Primary Objectives	Primary Endpoints

Evaluate ramucirumab safety following a single dose in healthy participants

	

Incidence of adverse events (AEs), treatment-emergent adverse events (TEAEs), and serious adverse events (SAEs) after intravenous (IV) administration and subcutaneous (SC) administration in healthy participants

Assess injection site reactions (ISRs) following SC administration of ramucirumab using ISR questionnaire

	

Characterization and measurement of incidence and severity of ISRs (including injection site pain [ISP]) using data collected from the ISR questionnaire

Assess ramucirumab PK following a single dose of IV or SC administration

	

PK parameters:

IV: area under the concentration versus time curve (AUC) from zero to infinity (<math>AUC_{[0-\infty]}</math>), maximum observed drug concentration (<math>C_{max}</math>), time of maximum observed drug concentration (<math>t_{max}</math>)

SC: <math>AUC_{(0-\infty)}</math>, <math>C_{max}</math>, <math>t_{max}</math> after SC administration

#### 4.2 Exploratory Objectives and Endpoints

Exploratory Objectives	Exploratory Endpoints

• Immunogenicity

	

• The frequency and percentage of participants with preexisting antidrug antibodies (ADA) and with treatment-emergent antidrug antibody positive (TE ADA+) to ramucirumab will be tabulated and any difference after IV administration versus SC administration

• For the TE ADA+ participants, the distribution of maximum titers will be described. The frequency of neutralizing antibodies will also be tabulated in TE ADA+ participants

• The relationship between the presence of antibodies and the PK parameters, including safety, to ramucirumab after IV versus SC administration

• Assess ISRs following SC administration of ramucirumab using Scarletred tool

	

• Characterization and measurement of incidence and severity of ISRs using data collected from the exploratory tool

#### 5. STUDY DESIGN

This is a single-site study in healthy participants who will receive a single dose of SC or IV ramucirumab. The study will be participant- and investigator-blinded, randomized, and placebo-controlled (7 ramucirumab:3 placebo per group/dose level). Placebo will be used as a comparator for both IV and SC to allow interpretation of safety and tolerability data following administration.

There will be sentinel dosing in this protocol, the initial 2 participants will be randomized/dosed (1 ramucirumab:1 placebo), and subsequently (the next day), the remaining participants in the group will be dosed. This will be subject to a satisfactory safety review by the investigator. This will occur on both the first dose of SC (Group 1).

Participants will be screened within 28 days prior to Day 1 of dosing for each group. Participants will be admitted to the clinical research unit (CRU) as part of an inpatient visit on Day -1 and will be sequentially enrolled. In each group, participants will be randomized to receive a single dose of IV or SC ramucirumab or placebo (7 ramucirumab:3 placebo per group).

The participants receiving ramucirumab in each group will be administered the following dose level (3 dose levels predicted to be ultimately used for therapeutic intent):

- Group 1 will test a ramucirumab 350-mg SC dose
  - administered at a concentration of 175 mg/mL as 1×2-mL injection.
- Group 2 will test a ramucirumab 700-mg SC dose
  - administered at a concentration of 175 mg/mL as 2×2-mL injections.
- Group 3 will test a ramucirumab IV dose (maximum of 350 mg)
  - administered as a 60-minute infusion (35 mL×10 mg/mL)
  - Analysis of safety and PK data from Groups 1 to 3 will allow initiation of Group 6.
- Group 4 will test a ramucirumab 350-mg SC dose
  - administered at a concentration of 87.5 mg/mL as 2×2-mL injections
  - The purpose is to investigate the effect of a different drug product concentration on PK and safety and Group 1 will be the reference comparison group.
- Group 5 will test a ramucirumab 350-mg SC dose
  - administered at a concentration of 175 mg/mL as 2×1-mL injections
  - The purpose is to investigate the effect of a different volume administered at the injection site on PK and safety and Group 1 will be the reference comparison group.
- Optional Group 6 may test SC ramucirumab dose, maximum 350 mg
  - administered at a concentration of 175 mg/mL administered via an infusion pump according to the pharmacy manual

The SC injection site will be the abdomen.

[figure not shown]
There will be at least a 2-week safety observation period between the titrating SC injection groups (Groups 1 and 2), and between the SC and IV 700-mg groups (Group 2 and 3) while local laboratory data is reviewed by the sponsor and investigator. If the safety review is acceptable, Groups 4 and 5 may be dosed simultaneously to Group 3, as no dose escalation is occurring in those groups. Group 6 will be dosed with an infusion pump once the sponsor has reviewed both the safety and PK data (Groups 1 through 3) and thus confirm the dose for Group 6 (maximum dose 1400 mg).

Following the safety review of Groups 1 and 2, the sponsor and investigator agreed to allow doses to be reduced for remaining groups. This may mean less groups may need to be studied. The asymptomatic transaminase increases observed during the safety review have also lead to a change in the exclusion criteria to further enhance the safety of the participants. In view of these findings, subsequent doses will be capped at 350 mg. Lower doses may also be studied. These decisions will be based on emerging data.

Injection site pain and ISRs will be monitored in each group, and a comparison of scorings will be used. The severity of ISP and ISRs reported across all participants will be evaluated. The data from Group 1, in comparison to Groups 4 and 5, will provide insight about the effect of injection volumes and ramucirumab concentration on ISP and ISR.

Participants will be discharged from the CRU on Day 8 after all study assessments have been completed and in agreement with the investigator. Participants may be required to remain in the CRU longer than Day 8, at the investigator's discretion. Participants will be required to return to the CRU for clinical assessments and blood samples on an outpatient basis until the final follow-up visit approximately 12 weeks following the IV infusion or SC injection.

The study schema is shown below.

## 6. TREATMENTS

The following is a list of the study treatment names that will be used in the TFLs.

Study Treatment Name	Abbreviations	Treatment order in TFL
Placebo IV	A	1
Placebo SC	B	2
350 mg ramucirumab IV	C	3
350 mg ramucirumab SC (1x2 mL)	D	4
350 mg ramucirumab SC (2x2 mL)	E	5
350 mg ramucirumab SC (2x1 mL)	F	6
700 mg ramucirumab SC (2x2 mL)	G	7
XX mg ramucirumab slow SC infusion	H	8

## 7. SAMPLE SIZE JUSTIFICATION

Approximately 60 participants will be enrolled and randomly assigned to study intervention (10 per group/dose level; 7 ramucirumab:3 placebo) to obtain at least 48 evaluable participants overall for an estimated total of at least 8 evaluable participants per intervention group (6 ramucirumab and at least 2 placebo). The sample size is not powered on the basis of statistical hypothesis testing. A participant will be considered evaluable when the participant completes up to 40 days of study procedures. When a participant does not complete up to 40 days of study procedures, the sponsor will be consulted if the participant will need to be replaced.

## 8. DEFINITION OF ANALYSIS POPULATIONS

The “Enrolled/Intent-to-Treat” population will consist of all participants assigned to treatment, regardless of whether they took any doses of study treatment, or if they took the correct treatment. Participants will be analyzed according to the treatment group to which they were assigned.

The “Safety” population will consist of all participants who received at least one dose of ramucirumab or placebo.

The “Pharmacokinetic” population will consist of all participants who received at least one dose of ramucirumab and have sufficient evaluable PK data.

All protocol deviations that occur during the study will be considered for their severity/impact and will be taken into consideration when participants are assigned to analysis populations.

## 9. STATISTICAL METHODOLOGY

### 9.1 General

Data listings will be provided for all data that is databased. Summary statistics and statistical analysis will only be presented for data where detailed in this SAP. For continuous data, summary statistics will include the arithmetic mean, arithmetic standard deviation (SD), median, minimum, maximum and N; for log-normal data (e.g. the PK parameters: AUCs and  $C_{max}$ ) the geometric mean and geometric coefficient of variation will also be presented. For categorical data, frequency count and percentages will be presented. Data listings will be provided for all participants up to the point of withdrawal, with any participants excluded from the relevant population highlighted. Summary statistics and statistical analyses will generally only be performed for participants included in the relevant analysis population. For the calculation of summary statistics and statistical analysis, unrounded data will be used.

Mean change from baseline is the mean of all individual participants' change from baseline values. Each individual change from baseline will be calculated by subtracting the individual participant's baseline value from the value at the timepoint. The individual participant's change from baseline values will be used to calculate the mean change from baseline using a SAS procedure such as Proc Univariate.

Data analysis will be performed using SAS® Version 9.4 or greater.

## 9.2 Demographics and Participant Disposition

Participant disposition will be listed. The demographic variables age, sex, race, ethnicity, body weight, height and body mass index will be summarized by treatment group and listed. All other demographic variables will be listed only.

## 9.3 Pharmacokinetic Assessment

### 9.3.1 Pharmacokinetic Analysis

PK parameter estimates will be determined using non-compartmental procedures in validated software program (Phoenix WinNonlin Version 8.1 or later).

Plasma concentrations of ramucirumab (LY3009806) will be used to determine the following PK parameters, when possible:

Parameter	Units	Definition
AUC(0-t last )	h*μg/mL	area under the concentration versus time curve from time zero to time t, where t is the last time point with a measurable concentration
AUC(0-∞)	h*μg/mL	area under the concentration versus time curve from time zero to infinity
%AUC(t last-∞ )	%	percentage of AUC(0-∞) extrapolated
C max	μg/mL	maximum observed drug concentration
t max	H	time of maximum observed drug concentration
t 1/2	H	half-life associated with the terminal rate constant (λz) in non-compartmental analysis
CL/F	L/h	apparent total body clearance of drug calculated after extra-vascular administration
CL	L/h	total body clearance of drug calculated after intravenous administration
V Z /F	L	apparent volume of distribution during the terminal phase after extra-vascular administration (SC administration only)
V Z	L	volume of distribution during the terminal phase after intravenous administration (IV administration only)
V ss /F	L	apparent volume of distribution at steady state after extra-vascular administration
V ss	L	volume of distribution at steady state following intravenous administration
F	%	bioavailability based on AUC(0-∞)
		$F = \frac{AUC [SC]}{AUC [IV]} \times 100$

Additional PK parameters may be calculated, as appropriate.

---

The software and version used for the final analyses will be specified in the CSR. Any exceptions or special handling of data will be clearly documented within the CSR.

Formatting of tables, figures and abbreviations will follow the Eli Lilly Global PK/PD/TS Tool: NON-COMPARTMENTAL PHARMACOKINETIC STYLE GUIDE. The version of the tool effective at the time of PK analysis will be followed.

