9.4.2. Pharmacokinetic Analyses

9.4.2.1. Pharmacokinetic Parameter Estimation

Pharmacokinetic parameter estimates for ramucirumab will be calculated by standard noncompartmental methods of analysis.

The primary parameters for analysis will be t_{max} , C_{max} , and AUC of ramucirumab following IV and SC administration and bioavailability following SC administration. Other noncompartmental parameters, such as half-life, IV clearance, volume of distribution, apparent clearance, and volume of distribution following IV and SC ramucirumab administration may be reported.

In addition to noncompartmental analysis, non-linear mixed-effect modelling analysis of the Study JVDT PK data will be performed. This model will enable to estimate mean and variability (variance) of ramucirumab PK parameters following SC administration and to investigate potential covariate explaining that variability.

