### 9.3.2 Pharmacokinetic Statistical Methodology

Ramucirumab bioavailability will be estimated. PK parameters will be evaluated to estimate ramucirumab  $AUC_{(0-\infty)}$  and  $C_{max}$  dose proportionality following SC administration in the dose range investigated. Log-transformed ramucirumab  $C_{max}$  and  $AUC_{(0-\infty)}$  parameters will be evaluated in a linear mixed effects model with fixed effects for dose (Groups 1, 4, and 5 who received 350 mg will be combined if appropriate). The treatment differences will be back-transformed to present the ratios of geometric means and the corresponding 90% confidence interval.

For ramucirumab SC dosing PK parameters, the  $t_{max}$  will be analyzed using a Wilcoxon rank-sum test. Estimates of the median difference based on the observed medians, 90% CIs, and p-values from the Wilcoxon test will be calculated to assess similarity or not in  $t_{max}$  between dose level groups 1, 4, 5 combined compared to group 2 and group 6.

The above-mentioned analysis investigating the relationship (e.g. linearity/proportionality) between ramucirumab PK parameters and dose may be adjusted/repeated in the event of significant difference in PK between the 350 mg SC groups (Group 1, 4, 5). Such difference would indicate significant impact of either injection volume or drug product concentration on the PK. In this scenario, the analysis, investigating the relationship (e.g. linearity/proportionality) between ramucirumab PK parameters and dose, may be repeated by excluding the data from one or two of the 350 mg SC group.

Comparison of  $AUC_{(0-\infty)}$ ,  $C_{max}$  and  $t_{max}$  between Group 1 and Group 4 will enable to assess the effect of changing the drug product concentration on the exposure. The log-transformed  $AUC_{(0-\infty)}$ ,  $C_{max}$  and  $t_{max}$  will be the response variable, and the drug product concentration (that is, Group 1 and Group 4) is the explanatory variable.

Comparison of  $AUC_{(0-\infty)}$ ,  $C_{max}$  and  $t_{max}$  between Group 1 and Group 5 will enable to assess the effect of changing the volume injected at one site of injection on the exposure. The log-transformed  $AUC_{(0-\infty)}$ ,  $C_{max}$  and  $t_{max}$  will be the response variable, and the volume injected (that is, Group 1 and Group 5) is the explanatory variable.

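### The SAP's bioavailability formula has no dose term, so for Group 2 (700 mg SC against at most 350 mg IV) it overstates dose-normalised F at least twofold.

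*SAP*

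**What the plan says.** The parameter table in SAP 9.3.1 gives the only formula for bioavailability in either document: "F = \frac{AUC [SC]}{AUC [IV]} \times 100". It is based on AUC(0-∞), whose unit in the same table is h*µg/mL, so dose has not been divided out. The same table also lists CL for the IV group and CL/F for the SC groups.

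The doses come from SAP 5 and SAP 6:

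- SAP 5: "Group 2 will test a ramucirumab 700-mg SC dose".
- SAP 5, the only IV group: "Group 3 will test a ramucirumab IV dose (maximum of 350 mg" being its cap. The same section adds for the remaining groups: "Lower doses may also be studied".
- SAP 6 names the IV treatment "350 mg ramucirumab IV" and leaves Group 6 open as "XX mg ramucirumab slow SC infusion".
- Groups 1, 4 and 5 each receive 350 mg SC.

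On estimation, SAP 9.3.2 says only "Ramucirumab bioavailability will be estimated". Protocol 9.4.2.2 refers back to 9.4.2.1, which has no formula but includes in its list of primary parameters "AUC of ramucirumab following IV and SC administration and bioavailability following SC administration". SAP 3 states that the SAP takes precedence over the protocol's statistical section, so the printed formula governs.

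**The concern.** Absolute bioavailability compares exposure per unit of dose. Leaving dose out is harmless only when the two doses are the same, and here they differ for Group 2. Nothing limits F to the 350 mg groups. Protocol 2.1 says that the SC dose-escalation groups serve to assess bioavailability, which brings the 700 mg group into scope.

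Protocol 4.2 presents bioavailability as the scientific aim of the study, and protocol 2 says the data will be used to recommend an SC regimen. A doubled F is plainly impossible only when the true value is above 50%. Below that it looks credible, and set beside Group 1 it would suggest that bioavailability rises with dose.

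There is a second gap. Each participant receives one route, so nobody has both an SC and an IV AUC. F must therefore be a comparison between groups, and the SAP does not say how that comparison is formed or what interval goes with it.

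**Working it through.** **Inputs**

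| Quantity | Value | Source |
|---|---|---|
| SC dose, Groups 1, 4, 5 | 350 mg | SAP 5 |
| SC dose, Group 2 | 2 × 2 mL × 175 mg/mL = 700 mg | SAP 5 |
| IV dose, Group 3 | at most 35 mL × 10 mg/mL = 350 mg | SAP 5, SAP 6 |
| Planning value of F | 0.60 (0.44 to 0.79) | Protocol 4.3 |
| Simulated AUCss over 2 weeks | SC 59, IV 48.0 mg.h/mL (medians) | Protocol Appendix 6 |
| 10 mg/kg in mg | 700 mg at 70 kg | Protocol 4.3, footnote b |

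**1. The protocol's own figure.** Appendix 6 reports a steady-state SC/IV AUC ratio of 1.23, and 59/48.0 = 1.229 reproduces it. Over two weeks the SC regimen delivers 2 × 700 = 1400 mg and the IV regimen 700 mg at 70 kg, a dose ratio of 2. The printed formula applied to these figures gives 123%. Dividing by dose gives (59/1400)/(48.0/700) = 0.615, close to the 0.60 that went into the simulation. At an assumed mean weight of 60 kg it is 0.527 and at 80 kg 0.702, so this illustrates the point and is not an exact recovery.

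**2. Size of the error.**

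printed F / dose-normalised F = [AUC(SC)/AUC(IV)] / [(AUC(SC)/dose SC)/(AUC(IV)/dose IV)] = dose SC / dose IV

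This holds whatever the variability or sample size. The IV doses below 350 mg are arithmetic illustrations only; the SAP permits lower doses but names none.

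| IV dose | Factor, Groups 1, 4, 5 | Factor, Group 2 | Group 2 F printed if dose-normalised F is 60% |
|---|---|---|---|
| 350 mg | 1.00 | 2.00 | 120% |
| 300 mg | 1.17 | 2.33 | 140% |
| 175 mg | 2.00 | 4.00 | 240% |

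At 350 mg IV, the planning range of 44% to 79% would be printed for Group 2 as 88% to 158%.

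**3. Consistency within the SAP table.** CL = dose IV/AUC(IV) and CL/F = dose SC/AUC(SC). Their ratio, CL ÷ (CL/F), is the dose-normalised F. With F = 0.60 and 350 mg IV, it gives 60% for both the 350 mg and the 700 mg SC dose. The printed formula gives 60% and 120%. For Group 2 the table therefore contains two incompatible values of F.

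**The case against.** The best defence is that the formula is shorthand, that any pharmacokineticist would dose-normalise, and that the report would expose a mistake. CL and CL/F are tabulated alongside. SAP 9.3.2 analyses dose proportionality separately, and protocol 9.4.2.1 adds a mixed-effects model. Protocol 4.3 treats 60% as a conservative planning value, and at or above it Group 2 would show at least 120%, which nobody would accept. The formula is right for three of the four SC groups whose dose is fixed. F appears in neither endpoint table, nothing is powered on it, and the raw data allow correction at any time. The table shells, which might restrict where F is shown, are not among the documents.

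Much of this is fair. The error would probably be noticed if F is near or above its planning value, and it is fully recoverable. But these are routes to discovery. None of them changes the written rule, and a parameter the protocol calls primary should not depend on a reader spotting an impossible value. If dose-normalisation is intended, writing it down costs one line.

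One technical qualification stands. The factor is exact against dose-normalised F. It equals the overstatement of true F only if clearance does not depend on dose, which the study itself sets out to examine.

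Nor is the problem only a by-product of the reduced IV dose. With the 700 mg IV dose originally planned (protocol 4.3), the same formula would have halved F for the 350 mg SC groups, since 350/700 = 0.5.

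**Conclusion.** The formula is wrong as written and should be corrected before the analysis. For Group 2 it exceeds dose-normalised F by 700 divided by the IV dose: exactly 2.0 at 350 mg IV and never less under the 350 mg cap. Groups 1, 4 and 5 are unaffected at 350 mg IV and become wrong only if the IV dose given is lower. Group 6 is affected if its dose differs from the IV dose. Reading the factor as bias in true F requires dose-linear clearance; the statement about dose-normalised F needs no assumption.

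**What to change.** In SAP 9.3.1, replace the formula with

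F = [AUC(0-∞) SC / dose SC] / [AUC(0-∞) IV / dose IV] × 100,

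using the doses actually administered, and state that it assumes dose-linear clearance. Name the SC groups for which F will be reported.

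In SAP 9.3.2, define the estimator: fit a linear model of log(AUC(0-∞)/dose) on treatment group, take each SC-minus-IV contrast, and back-transform it with a 90% CI, as for the other PK comparisons in that section.

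The cost is one formula, one sentence and a few lines of code. No data are added and no dose changes. At 350 mg IV, the reported F for Group 2 halves and Groups 1, 4 and 5 stay as they are.

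The interval is useful because the groups are small. As an illustration, take log-SDs from the Appendix 6 AUCss percentiles: ln(75/30)/3.29 = 0.28 (IV) and ln(102/34)/3.29 = 0.33 (SC). Assume five active groups with a pooled variance, giving 25 df with 6 per group or 30 df with 7. The 90% CI around F = 60% is 60% ×/÷ exp(t × SD × √(2/n)):

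| n per group | log-SD 0.28 | log-SD 0.33 |
|---|---|---|
| 6 | 45.5% to 79.1% | 43.3% to 83.1% |
| 7 | 46.5% to 77.4% | 44.5% to 80.9% |

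These spreads come from a repeat-dose simulation in patients, so the actual widths may differ.
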